Surgical cases requiring sedation by an anesthesia provider, also known as monitored anesthesia care (MAC), are a popular choice for outpatient surgical procedures with benefits of “less physiologic disturbance and a more rapid recovery than general anesthesia” (Das 2015). However, MAC cases still come with risk: per the American Society of Anesthesiologists closed claim database, “the most common malpractice claim is inadequate oxygenation/ventilation, with more than 80% of claims of this nature resulting in brain damage or death” (McMurray 2020). Since 1908, anesthesia providers have been utilizing interventional airway devices that manipulate the soft tissues of the nasopharynx, oropharynx, and hypopharynx to relieve obstruction to support patient ventilation and oxygenation; however, there are few studies that directly compare the efficacy & side effect profiles between these devices (Matioc 2019). Additionally, a recent survey indicates that many anesthesia providers desire an alternative airway intervention device than the current ones most commonly used in current practice (McMurray 2020). We will examine the possibility of using at-home, over-the-counter anti-snoring devices as an intraoperative airway device.

STUDY ENDPOINTS:

PRIMARY ENDPOINT: Combined total number of airway interventions during an anesthetic sedation case – including head tilt/rotation, mandible thrust, chin lift, shoulder lift, neck extension or flexion, tongue pull.

SECONDARY ENDPOINTS:

- Satisfaction of Anesthetist via survey
- Maximum/minimum end-tidal CO₂
- # of times SpO₂ value < 92%
- % of time during the case SpO₂ < 92%
- maximum/minimum SpO₂ value
- EKG analysis that were not recorded as “Normal Sinus rhythm”:
- Heart rate maximum & minimum
- maximum/minimum Systolic, diastolic, and mean blood pressure
- Total dose and type of hypnotic & narcotic given
- Case type
- Case duration
- Baseline characteristics (Age, Gender, BMI)

- Time spent in Phase 2 PACU Recovery
- Adverse events (i.e. regurgitation and aspiration, bronchospasm, cough, case converted to GA)

STUDY INTERVENTION(S) / INVESTIGATIONAL AGENT(S):

We will use anti-snoring appliance devices (specifically the FDA approved Zyppah) to attempt to relieve tissue obstructions that cause snoring during sleep. The application of the devices to the body is less invasive than other common intraoperative rescue airway devices (e.g. nasal trumpets and oral airways) which are not designed to be patient specific.

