We will be purchasing the device from the manufacturer's website. We will be purchasing the devices via funds awarded by the James E. Eckenhoff Residents' Research Award.

The device will be stored in the PI's key-locked office, until it is given to a research team member to be given to a subject after recruitment and prior to their procedure. Research personnel will bring the appliance to the preoperative holding area & will help mold it for the patient, and will insert it prior to transport to the operating suite. The device will remain in place until the completion of procedure, unless the anesthesia provider in the room feels it needs to be removed for any reason. The patient or anesthesia personnel can remove the device at their leisure after completion of the procedure.

PROCEDURES INVOLVED:

The study participants will be recruited into two groups: patients wearing an anti-snoring appliance device during an anesthetic sedation procedure; and those who do not wear an anti-snoring device. To ensure anesthetic providers have easy access to the patient's airway for standard of care manipulation (if needed), the patients eligible for this study would be those who are undergoing procedures below the umbilicus (e.g. gynecological, urological, orthopedic, etc.) in addition to having a STOP-BANG score of 2 or greater. This will ensure patient safety and provide a wide demographic of potential subjects to increase the generalizability of the study.

For both patient groups, the study procedure is the same. Eligible patients will be identified by chart review of various elements of the electronic medical record, as follows:

Patients will be identified and be seen by the study team in the pre-operative clinic on 17th floor Lavin and in the holding area to interview individuals who are to undergo eligible anesthetic sedation procedures as above. If the patient agrees to participate in the study, they will be randomized at that time to one of the two groups (anti-snoring appliance device to be used for procedure or not).

The groups in the prospective, randomized, controlled trial in patients undergoing anesthetic sedation procedures will be as follows:

Group #1: Anti-snoring appliance (Zyppah) that will be utilized during their procedure
Group #2: Control group, that will not utilize anti-snoring appliance

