Participants will be randomized to treatment groups based on a random computer-generated (<https://www.randomizer.org>). Anesthesia providers will not be blinded to randomization, and research personnel will observe the procedure to collect all outcome measures in this study.

For group 1, the study team will aid them in molding and preparing the device in the pre-operative area. Anesthesia providers will be instructed on how the device works and when to place it (with aid from the research team) in addition to receiving a question and answer sheet and protocol they can follow to take with them to the operating room. Prior to the administration of anesthetic medications, the patient will be aided in inserting the device, and wear it throughout the entirety of the case. Regardless of the group, from the start of sedation until the patient leaves the procedure suite. When an anesthesia provider believes they make a clinically significant airway intervention (either via jaw lift, head turning, etc.) they will be instructed to use the “mark now” icon in the anesthetic record and utilize the free text to indicate what intervention was done and why.

All standard practices and standard monitors for anesthetic sedation cases will be utilized.

A post-survey will be administered to anesthesia providers in group 1 to gauge satisfaction.

Anesthetic record will be reviewed by research team members following the end of the case.

DATA AND SPECIMEN BANKING

We will collect data including reason for procedure, type of procedure, and patient demographics (including medical history, sex, age, and weight); in addition to data collected via electronic chart review including: Documented Obstructive Sleep Apnea (OSA), date of procedure, surgical case length, anesthesia type requested, anesthesia type documented, Provider team staff composition, documented neuraxial or nerve block procedure (if applicable), “in room” time, max/min heart rate, min/max oxygen saturation, number of instance oxygen saturation fell below 92%, % of time during case where oxygen saturation was below 92%, min/max end tidal CO₂, min/max blood pressure, total dose of hypnotic & narcotic given, “out of room” time, adverse events noted in charting, free-text written by providers, and total hospital length of stay.

SHARING RESULTS WITH PARTICIPANTS

Results will not be shared with participants.

STUDY TIMELINES

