Individual subjects and anesthetic providers will participate in the study for the duration of their procedure requiring anesthetic sedation. It will take approximately 3 months to enroll participants and approximately 3 months to perform data analysis.

INCLUSION AND EXCLUSION CRITERIA

Inclusion criteria

Adult patients (age 18-89 years old)

Undergoing procedures below the umbilicus requiring anesthetic sedation without an invasive airway

STOP-BANG score of 2 or greater.

English or Spanish language speaking

Exclusion criteria

Patients requiring general anesthesia.

Sleep apnea

Serious breathing or respiratory disorders such as COPD, asthma, emphysema

Poor dental health including severe gum disease, loose teeth, abscess, mouth sores, bleeding gums

Dental implant place within last 3 months

TMJ disorder

Mouth or jaw pain

Full dentures

Wear braces

Sleep with CPAP or other devices

Other special populations (individuals who are not yet adults, prisoners, vulnerable populations, pregnant) will also be excluded.

VULNERABLE POPULATIONS:

Will not be a part of study.

PARTICIPANT POPULATION(S)

Accrual Number:	Category/Group: (Adults/Children Special/Vulnerable Populations)	Consented: Maximum Number to be Consented or Reviewed/Collected/Screened	Enrolled: Number to Complete the Study or Needed to Address the Research Question
Local	Adults	28	28
Study-wide		28	24
Total:		28	24

RECRUITMENT METHODS

Patients undergoing an eligible procedure requiring anesthetic sedation will be identified by the anesthesiology team by chart review and the schedule in the pre-operative clinic on the 17th floor Lavin pavilion prior to their procedure. They may also be approached by the research team the morning of their procedure for possible enrollment into the study. If the potential subject is interested in the study a study team member will ask for the subject's email address to send an Econsent using REDCap for their review.

The source of participants will be NMH pavilions (Galter, Feinberg, Lavin) in addition to Prentice Women's Hospital.

COMPENSATION FOR PARTICIPATION IN RESEARCH ACTIVITIES

There will be no compensation for participation; however, patients who are randomized into one of the anti-snoring device groups will be allowed to keep the device, if they wish.

WITHDRAWAL OF PARTICIPANTS

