We utilized a study by Qiansong Xiao et al titled “Comparison of Nasopharyngeal Airway Device and Nasal Oxygen Tube in Obese Patients Undergoing Intravenous Anesthesia for Gastroscopy: A Prospective and Randomized Study”, which compared the oxygen saturation levels in patients who did or did not have an invasive nasopharyngeal airway at the beginning of the anesthetic sedation procedure, to perform our power analysis. 260 patients were included and randomized; with 3 patients excluded due to failure of the nasopharyngeal airway. Based on the differences in “change in SpO₂” and “raising the mandible” between their test and control groups, and power analysis was completed with an alpha value of 0.05 and power value of 80%. The n per group that was calculated to provide the appropriate power to identify a statistical difference was 12 patients per study group. To compensate for patients in our study being less obese we increased the number per group to 14 subjects. We plan to approach 28 subjects and randomize 28 patients to 2 groups, allowing for patients who may not end up getting their procedure or instances where data collection is incomplete or absent.

Statistical analysis: Data will be compared between all groups using paired t-test with p< 0.05 required to reject the null hypothesis.

Data Security:

All collected data will be stored in REDcap using NM password protected computers for data entry. Data in REDcap is backed up nightly using NM servers which are only accessible to the NM IT administrator. Paper documents generated during the study will be stored in Arkes Pavilion 10th floor Department of Anesthesiology locked research cabinet. Data both paper and electronic will be destroyed 5 years after the completion of the study using current department policy and approved vendors.

PROVISIONS TO MONITOR THE DATA TO ENSURE THE SAFETY OF PARTICIPANTS N/A

PROVISIONS TO PROTECT THE PRIVACY INTERESTS OF PARTICIPANTS

Patients in this study undergoing a procedure under anesthetic sedation can be stressful. If a subject does not feel comfortable with participating, they will have the option to opt out at any time and it will not impact their care if they choose to do so.

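### Block cases are eligible and recorded, but the primary comparison ignores block status; a prespecified covariate and a sentence on the power assumption would help

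*Combined protocol and SAP*

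**What the plan says.** All references are to the combined protocol and SAP.

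- **Who is eligible.** The inclusion criterion is "Undergoing procedures below the umbilicus requiring anesthetic sedation without an invasive airway". By type of anesthetic, the only exclusion is "Patients requiring general anesthesia". Neither list mentions blocks. Procedures Involved describes the case mix as "procedures below the umbilicus (e.g. gynecological, urological, orthopedic, etc" and presents the breadth as deliberate, for generalizability.
- **What is recorded.** Data and Specimen Banking lists "documented neuraxial or nerve block procedure (if applicable" as a chart-review item. The requested and the documented anesthesia type are separate items.
- **Allocation.** "Participants will be randomized to treatment groups based on a random computer-generated". No strata are named.
- **Primary endpoint.** "Combined total number of airway interventions during an anesthetic sedation case".
- **Analysis.** Data Statistics names a t-test at p < 0.05, with no covariate.
- **Sizing.** Alpha is 0.05 and power 80%, giving 12 per group, based on a randomized study in "Obese Patients Undergoing Intravenous Anesthesia for Gastroscopy". The rise to 14 is attributed to less obese patients, and the 28 is also said to cover cancelled procedures and missing data. Neither allowance is tied to block use.

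**The concern.** The endpoint is a count of airway maneuvers under sedation. A neuraxial or nerve block can supply the surgical anesthesia, so sedation might be lighter and maneuvers fewer in either arm. If so, block patients would have little room to benefit. Mixing them in would lower the average difference, and the gap between block and non-block patients would add variance that a plain t-test leaves in the error term. With 14 per arm, the two kinds of patient could also split unevenly by chance.

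The sizing source used intravenous anesthesia for a different procedure, so its figures carry no visible allowance for such a mix. At stake are the power of a very small trial and the ease of interpreting its single result.

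**Working it through.** **1. The plan's figure.** No difference, SD or rate is given, so 12 per group cannot be reproduced forward. Inverting it (two-sided alpha assumed, as sidedness is not stated):

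d = √(2/12) × (1.960 + 0.842) = 1.144 by the normal approximation, or 1.197 by noncentral t.

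At d = 1.144, power with 14 per group is Φ(1.144 × √(14/2) − 1.960) = Φ(1.066) = 86%, if all 28 contribute.

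**2. Possible dilution.** Let f be the share of block cases. Assume no device effect in them and an unchanged SD:

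power = Φ(1.144 × (1 − f) × √7 − 1.960)

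| f (assumed) | Power, 14 per group | n per group for 80% |
|---|---|---|
| 0 | 86% | 12 |
| 10% | 78% | 15 |
| 25% | 62% | 22 |
| 50% | 33% | 48 |

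A count model gives the same pattern. With Poisson means 3 v 1.25 without a block, 0.3 in both arms with one, and an unpaired t-test, power at 14 per group is 87%, 76%, 57% and 30% at the same shares. At the other extreme, if block patients have the same mean and the same benefit as the rest, power stays at 86–87% whatever their share.

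**3. What adjustment and stratification each contribute.** Simulated power at 14 per group, with non-block patients N(1.5, 1) in control v N(0.3, 1) with the device, and every block patient at exactly zero:

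| Block share | Neither | Stratified list only | Block term only | Both |
|---|---|---|---|---|
| 25% | 66% | 66% | 73% | 72% |
| 33% | 58% | 58% | 66% | 67% |
| 50% | 39% | 36% | 50% | 52% |

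These figures move by a few points between simulation runs. The covariate does nearly all the work.

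The gain depends on how well block status predicts the count:
- Block patients with mean 0.3, SD 1 and no device effect: stratifying and adjusting moves power only from 58% to 61%, 48% to 49%, and 29% to 30%.
- Block patients with mean 0.9, which is the average of 1.5 and 0.3: no change beyond simulation error.
- Poisson counts with lower means in block patients: the gain from adjusting, without stratifying, is about 7 to 16 points.

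In every scenario above in which block patients have no device effect, adjusted power at these shares remains below 80%.

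**4. Chance imbalance.** With K block patients among 28 split at random into 14 v 14 (hypergeometric), the probability that the arms differ by 4 or more block patients is 0.21 for K = 8, 0.24 for K = 10 and 0.26 for K = 14.

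As an illustration with no device effect and K = 10, a split of 7 device to 3 control creates an apparent benefit of 1.5 × (7 − 3)/14 = 0.43 SD. The unadjusted test is then significant about 11% of the time, against about 0.5% when the split is 5:5. Those are rates given one split. Over all random splits the imbalance adds no bias and does not inflate the type I error.

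**The case against.** The strongest objection is that the harm is assumed. The documents give no block share and no count in block patients, and do not say that such patients are more lightly sedated. The words about applicability show only that a block may occur, and every participant must need sedation and have a STOP-BANG score of 2 or more. This stands: the loss ranges from none to severe. A reader might infer that block cases do dilute the effect, but the documents do not support that as fact.

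A reader might also infer that an uneven split would bias the result. It would not: randomization covers chance imbalance on average, and the cost is precision and interpretability. The same holds for BMI, case type or duration. Block status is singled out because it bears on the anesthetic itself and is already collected.

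It is also fair that separate lists add little power, that adjustment cannot restore a diluted average effect, and that breadth was chosen for generalizability. The fix therefore excludes nobody and treats stratification as optional.

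Finally, the requested anesthesia type may not show a planned block at the moment of assignment, which can occur in the pre-operative clinic. That needs confirming.

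None of this removes the core: an anesthetic variable that plausibly predicts the endpoint is recorded and then left out of the comparison.

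**Conclusion.** The point holds in conditional form. Block cases are eligible, their status is recorded, and the primary comparison ignores it. If they need fewer interventions, power at 14 per group could fall from about 86% to 78% at a 10% block share and to 33% at 50%, given no device effect in block cases and the d of 1.144 implied by 12 per group. If they do not differ from other patients, nothing is lost. The gain from adjustment runs from nil to about 16 points, depending on how strongly block status predicts the count.

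It is tempting to say that the 80% figure assumes no block cases. The plan gives no sizing inputs, so that cannot be shown. What can be said is that the source patients had intravenous anesthesia for gastroscopy and that no allowance for blocks is stated. Block use is one part of a wider mismatch with the source study, which also differs in obesity and procedure. This is a cheap improvement to precision and clarity, not a flaw that invalidates the comparison.

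**What to change.** 1. Record planned neuraxial or nerve block (yes/no) before assignment. Confirm that the requested anesthesia type captures it; if not, add one item.
2. Prespecify planned block as a covariate in the primary between-group comparison of intervention counts, and show counts by arm and block status descriptively. Stratifying the list by planned block is optional and adds little power. (The paired form of the named t-test, for two independent groups, is a separate matter.)
3. State in Data Statistics that the 12-per-group figure comes from patients under intravenous anesthesia for gastroscopy and makes no allowance for block cases, so power may fall below 80% depending on the block share. Give the expected share if it is known.

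**Cost:** possibly one data item, one model term, one degree of freedom and a less favorable power statement; no extra patients. There is little gain if block status does not predict the count. Adjustment recovers precision only; countering dilution would need a restricted population or a larger trial.

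### The stated 80% power was taken from two outcomes of another study and is not shown for the primary endpoint, the combined count of airway manoeuvres; the direction of the error is unknown

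*Combined protocol and SAP*

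**What the plan says.** **Sizing.** The Data Statistics section, under Data Management and Confidentiality, bases the calculation on one external randomised study of a nasopharyngeal airway in obese gastroscopy patients: "Based on the differences in “change in SpO₂” and “raising the mandible” between their test and control groups". It reports that a "power analysis was completed with an alpha value of 0.05 and power value of 80" (per cent), and then: "The n per group that was calculated to provide the appropriate power to identify a statistical difference was 12 patients per study group". The number is raised to 14: "To compensate for patients in our study being less obese we increased the number per group to 14 subjects". The same paragraph also presents the total of 28 as "allowing for patients who may not end up getting their procedure or instances where data collection is incomplete or absent". No difference, standard deviation or rate is given for either sizing outcome.

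**Primary endpoint.** Study Endpoints defines it as "Combined total number of airway interventions during an anesthetic sedation case" and lists six items: head tilt or rotation, mandible thrust, chin lift, shoulder lift, neck extension or flexion, and tongue pull. No expected mean, standard deviation or difference is given for this count.

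**SpO₂.** The secondary endpoints are the number of times below 92%, the percentage of case time below 92%, and the maximum and minimum. Data and Specimen Banking repeats these ("max/min heart rate, min/max oxygen saturation, number of instance oxygen saturation fell below 92" per cent, and so on). Neither place lists a change in SpO₂ or a pre-sedation value.

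**Recording of manoeuvres.** Under Procedures Involved, providers mark each clinically significant intervention in the anesthetic record and enter in free text what was done and why. That free text is among the data to be collected.

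**The concern.** A power figure belongs to a particular outcome, effect and variance. Here it was derived for two outcomes, and the trial will be judged on a third. One sizing outcome survives only as one of six parts of a sum. The other, a change in SpO₂, matches none of the listed SpO₂ summaries.

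With 28 patients a non-significant result is quite possible. A reader would then weigh it against an 80% chance of detecting the assumed effect, although no such chance was ever worked out for the count and no assumed effect on the count is stated. A null result could be taken as stronger evidence against the device than it is.

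**Working it through.** **1. Can the 12 per group be reproduced?** No. The inputs given are alpha 0.05, power 80% and n = 12; no difference, SD or rate is stated. One can only solve backwards for what 12 per group implies. I take alpha as two-sided (the section does not say) and compare independent groups, since the arms contain different patients.

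- Normal approximation: d = (1.960 + 0.842) × √(2/12) = 1.144.
- Independent-groups t-test, solved exactly: d = 1.197.
- One-sided versions: 1.015 (normal) and 1.048 (t).
- If raising the mandible was analysed as yes/no, 12 per group without continuity correction corresponds to differences such as 60% vs 7–8% or 80% vs 24–25%.

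The documents do not show which of these, if any, was used.

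**2. What the planned numbers can detect on any roughly continuous outcome** (80% power, two-sided 0.05, independent-groups t-test):

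| n per group | detectable d |
|---|---|
| 12 | 1.20 |
| 14 | 1.10 |

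**3. Does power on one component carry over to the sum?** Assume d = 1.197 on the mandible item. Let the other five items together have variance v times that of the mandible item, be independent of it, and carry a fraction f of its standardised effect. The standardised difference on the count is

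D = 1.197 × (1 + f√v) / √(1 + v).

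Power at 14 per group by the t-test:

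| v | D, f = 0 | power | D, f = 0.5 | power |
|---|---|---|---|---|
| 0.5 | 0.977 | 70% | 1.323 | 92% |
| 1 | 0.846 | 58% | 1.269 | 90% |
| 2 | 0.691 | 42% | 1.180 | 85% |

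Worked example for v = 1: with f = 0, D = 1.197/√2 = 0.846; with f = 0.5, D = 1.197 × 1.5/√2 = 1.27. For comparison, the mandible item alone at d = 1.197 has 86% power at 14 per group.

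**4. A second model as a check.** Take six items of equal SD with common correlation ρ, d = 1.144 on the mandible item and f × 1.144 on each of the other five. Then D = 1.144 × (1 + 5f)/√(6 + 30ρ). Normal-approximation power at 14 per group, for ρ from 0 to 0.6:

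- f = 0: D from 0.467 to 0.234, power 23% to 9%.
- f = 0.5: D from 1.635 to 0.817, power 99% to 58%.
- f = 1: power 96% or more.

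Both models put the power of the count on either side of 80%. The result turns on how far the other manoeuvres respond, how variable they are and how they correlate. The documents give none of these.

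**The case against.** The strongest reply is that the sizing outcomes are close relatives of the endpoints. Mandible thrust is part of the primary count and minimum SpO₂ is a secondary endpoint. The protocol says there are no large published studies of these devices under monitored anesthesia care, and borrowing from a neighbouring trial is common when direct data are lacking. All six manoeuvres relieve obstruction, which is what the device is meant to reduce, so the count may well respond more strongly than one component.

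Much of this stands, and it limits the point in three ways.

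- A reader might infer that the trial is underpowered for its primary endpoint. The documents do not support that. The low figures above require the other five manoeuvres not to respond at all, and nothing in the protocol says so.
- A reader might infer that the trial cannot check the assumptions it was sized on. For the mandible outcome that is wrong: the planned free-text entries allow a mandible count to be extracted. It is simply not named as an endpoint, so extracting it later would not be prespecified.
- The documents do not define the external study's change in SpO₂. That it needs a pre-sedation value is a reasonable reading, not an established fact.

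Whether unblinded providers might adjust oxygen differently by arm is a separate question and has no bearing on the sample-size basis.

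The reply does not supply a power basis for the count. Related outcomes can justify a rough choice of n, but they do not transfer the 80%.

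**Conclusion.** The point holds in limited form: the 80% power is unsupported for the primary endpoint, and neither sizing outcome is itself a listed endpoint. The 80% also attaches to 12 per group; the step to 14 has no calculation and is explained both by lower obesity and by possible losses.

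The size of the gap cannot be fixed from the documents. Under the assumptions shown, power on the count at 14 per group ranges from about 42–70% if the other manoeuvres do not respond to about 85–92% if together they carry half the standardised effect. These figures rest on an assumed d of 1.197 for the mandible item, independent components, assumed variance ratios and a two-sided test. They show that the power does not carry over; they do not estimate it. What can be stated without assumptions about the components is the detectable standardised difference: about 1.10 at 14 per group, or 1.20 if only 12 per group complete, which matches the 24 completers in the study-wide row of the accrual table.

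**What to change.** 1. **Data Statistics.** State that the 80% was taken from the external study's outcomes and was not calculated for the combined count. Give instead the standardised difference detectable with 80% power by a two-sided independent-groups t-test: about 1.10 at 14 per group and 1.20 at 12 per group.
2. **Study Endpoints, mandible count.** Name the mandible thrust/chin lift count, extracted from the entries already planned in the anesthetic record, as a separately reported secondary endpoint.
3. **Study Endpoints and Data and Specimen Banking, SpO₂.** Record SpO₂ just before sedation from the standard monitors and report the fall to the lowest value as a secondary endpoint. Do not claim that the 80% applies to it, since the external study's definition is not given and the 12 per group cannot be reproduced.

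Cost: some protocol wording and one added data field, with no more patients. The downside is that the stated power becomes less favourable, because the protocol would no longer claim 80% for its primary endpoint.

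### The two extra patients per group are assigned both to a less obese population and to losses, neither is quantified, and the accrual table gives both 28 and 24 as the number to complete or needed

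*Combined protocol and SAP*

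**What the plan says.** The power paragraph under Data Management and Confidentiality (Data Statistics, Preparation) takes differences in two variables, change in SpO₂ and raising the mandible, from a published trial of a nasopharyngeal airway. It uses alpha 0.05 and 80% power and reports: "The n per group that was calculated to provide the appropriate power to identify a statistical difference was 12 patients per study group". It then gives a reason for going higher: "To compensate for patients in our study being less obese we increased the number per group to 14 subjects". The next sentence reads "We plan to approach 28 subjects and randomize 28 patients to 2 groups", and continues "allowing for patients who may not end up getting their procedure or instances where data collection is incomplete or absent".

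The Study Summary also gives a sample size of 28. The accrual table under Participant Population(s) sets the maximum consented at 28 in every row. Its last column, headed in part "Number to Complete the Study or Needed to Address the Research Question", shows 28 for Local but 24 for Study-wide and for Total. The section on multi-site research is marked not applicable.

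Under Procedures Involved, patients who agree to take part are told apart at once: "they will be randomized at that time to one of the two groups". Under Withdrawal of Participants, the data of anyone who withdraws are deleted. The analysis sentence is: "Data will be compared between all groups using paired t-test with p< 0.05 required to reject the null hypothesis".

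**The concern.** The whole step from 12 to 14 per group is credited to the less obese population. The following sentence credits the resulting 28 to losses as well, and nothing is added. A patient whose procedure is cancelled or whose data are missing cannot also help to detect a smaller effect.

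No other buffer exists. Randomization takes place when the patient agrees, possibly in the pre-operative clinic before the day of surgery, so a cancelled procedure costs a randomized patient. The cap of 28 consented leaves no room to replace that patient.

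The accrual table does not settle which purpose was meant. The figure 24 fits a plan in which the extra patients are there to be lost. The figure 28 fits a plan in which all of them are needed.

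The stake is how a null result would be read. The plan does not say how many evaluable patients it needs, or what difference in the total number of airway interventions that number could detect.

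**Working it through.** **Inputs from the protocol.** Alpha 0.05 (sidedness not stated), power 80%, 12 per group calculated, 14 per group planned, 28 approached, randomized and at most consented, 28 or 24 to complete or needed. Not given: effect size, SD or rates behind the 12, expected loss, expected reduction in effect.

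**The plan's own sums.** 12 + 2 = 14, 2 × 14 = 28 and 2 × 12 = 24. All are right, and the last two are the two figures in the accrual table. The 12 itself cannot be reproduced because its inputs are not reported.

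**Assumptions for the rest.** Two-sided independent two-sample t-test at 0.05, equal SDs, approximate normality. With n per group and a difference of d SD, power is the probability that a noncentral t with 2n − 2 degrees of freedom and noncentrality d·√(n/2) falls outside ± the 97.5% point of the central t.

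**Step 1: difference detectable with 80% power.**

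| Evaluable per group | d (SD) |
|---|---|
| 11 | 1.256 |
| 12 | 1.197 |
| 13 | 1.145 |
| 14 | 1.100 |

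**Step 2: reduction in effect that still leaves 80% power.** The reduction covered is 1 − d(n)/d(reference). The reference is d(12) if 12 per group gave exactly 80%. It approaches d(11) if 12 was rounded up from just above 11.

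| Losses per group | Evaluable per group | Covered, 12 exact | Covered, rounding case (upper limit) |
|---|---|---|---|
| 0 | 14 | 1 − 1.100/1.197 = 8.1% | 1 − 1.100/1.256 = 12.4% |
| 1 | 13 | 1 − 1.145/1.197 = 4.3% | 1 − 1.145/1.256 = 8.8% |
| 2 | 12 | 0% | 1 − 1.197/1.256 = 4.7% |

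**Step 3: power when both happen.** The true difference is the reference d × (1 − reduction). The figure in brackets is the upper limit from the rounding case.

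| Effect smaller by | 14 per group | 13 per group | 12 per group |
|---|---|---|---|
| 0% | 86% (89%) | 83% (87%) | 80% (84%) |
| 4% | 83% (87%) | 80% (84%) | 77% (81%) |
| 8% | 80% (84%) | 77% (81%) | 73% (77%) |
| 10% | 78% (82%) | 75% (79%) | 71% (75%) |
| 20% | 68% (73%) | 65% (69%) | 61% (65%) |

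If the full reduction that 14 per group can cover (8.1%, or 12.4% in the rounding case) meets two losses per group, the true difference is 1.100 SD with 12 per group. Power is then 73% under either reference.

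**Step 4: numbers if both allowances were wanted in full.** Take 14 evaluable per group as the need (an 8% smaller effect, 12 exact) and divide by 1 − loss.

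- 5% loss: 14/0.95 = 14.7, so 15 per group, 30 in total.
- 10% loss: 14/0.90 = 15.6, so 16 per group, 32 in total.
- 2-in-14 loss: 14/(12/14) = 16.3, so 17 per group, 34 in total.
- 20% loss: 14/0.80 = 17.5, so 18 per group, 36 in total.

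All exceed 28. These are illustrations under assumed losses; no single required size follows from the protocol.

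**The case against.** **The plan never says that either allowance is complete.** It speaks of compensating and allowing for, with no rate for either, and a partial split does work: 13 evaluable per group with a 4% smaller effect keeps 80%. This stands. A reader might infer that 28 is claimed to give 80% power after full allowance for both, but the text does not say so. What remains is that two unquantified allowances share one reserve.

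**The sums are right.** This also stands. The point is an inconsistency in the sample-size rationale, not an arithmetic error.

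**The table column has two meanings.** Its header covers the number to complete or the number needed, so 24 may be the number needed and 28 the number hoped for. A reader might take 24 as the expected number of completers; the header does not establish that. The rows still have to agree, because one column of a trial that is not multi-site should not give different local and study-wide figures.

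**The size is conditional.** The 73% for an 8% smaller effect rests on 12 per group giving exactly 80%; with rounding it can be as high as 77%. That is why a range is shown.

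**The basis of the 12 is not unrelated to the primary endpoint.** Raising the mandible resembles the mandible thrust counted in that endpoint. That is fair, but the protocol reports no effect size or SD for the combined count.

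**Conclusion.** The point holds as an inconsistency in the sample-size rationale. The same two patients per group carry two purposes, neither is quantified, and the accrual table supports both readings. The reserve can cover one purpose or part of each, not both in full.

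Under a two-sided independent t-test at 0.05 with 12 per group giving exactly 80%, the increase offsets an effect about 8% smaller with no losses, 4% with one loss per group and none with two. The upper limits are 12%, 9% and 5% if 12 was rounded up from just above 11. An 8% smaller effect with 12 evaluable per group gives 73% power, up to 77% in the rounding case.

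A reader might go further and call the trial underpowered, or the 12 per group wrong. The protocol does not support that. Without the effect size and SD, the 12 is neither confirmed nor refuted. The text is clear on the double use; the size of any shortfall is not known.

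**What to change.** Keep 28 randomized and change the following.

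1. **Give the two extra patients per group one stated purpose**, chosen by the investigators, and say that the other is not allowed for. Alternatively, quantify a split (for example, one loss per group and a stated smaller reduction in effect).
2. **Make the three accrual rows agree with that choice.** If the extra patients are for losses, all rows show 24 needed and one cell changes (Local). If they are for a smaller effect, all rows show 28 needed and two cells change (Study-wide and Total). A split of one and one would show 26.
3. **Restate power as a detectable difference.** Suggested content: 80% power for a difference of about 1.20 SD in the total number of airway interventions with 24 evaluable patients, and about 1.10 SD with 28. Label it as assuming a two-sided independent two-sample t-test at 0.05, equal groups, equal SDs and approximate normality. Say that the 12 was derived from the published trial's variables. Do not write that 14 per group covers an 8% smaller effect without giving the assumption behind it.
4. **Replace the paired t-test** with a two-sided independent two-sample t-test between the two groups. Patients are randomized individually to separate groups and no pairing is described, so the analysis should match the power statement.

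If both allowances are wanted in full, state the assumed loss and effect reduction, recalculate, and raise the maximum consented.

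The cost is one paragraph, one test name and one or two table cells (three for a split), with no extra patients unless both allowances are kept in full. The downside is that the stated power becomes less favourable, because the plan must say openly which risk it does not cover or covers only in part.
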